peroperative 5th, 10th, 15th, 30th, 60th, 90th, 120th, 180th minute, and post-extubation heart rate, supravascular pressure, intravascular pressure, SpO₂, ETCO₂, and BIS values will be recorded.

Patients will be randomly assigned to two separate groups using a sealed envelope method, regardless of their demographic and surgical characteristics. In the ESP Block group, with the patient in the prone position, the research anesthesia team, following aseptic and antiseptic rules, will insert a linear probe (Hitachi Aloka Prosound F31) with a depth of 2-4 cm and a frequency of 10-15 mHz, approximately 2-3 cm lateral to the spinous process, one level above the operative level, in the parasagittal plane, under USG guidance (Hitachi Aloka Prosound F31). After visualizing the transverse process using an in-plane approach, a 50 mm long block needle (Braun Stimuplex® D 0.22 Gax2 in.50mm, Braun, Germany) will be inserted through the skin, passing through the trapezius and erector spinae muscles. When the needle reaches the transverse process (approximately 2-3 cm deep), a test dose of 0.5-1 mL of 0.9% NaCl will be administered between the erector spinae fascia and the vertebral transverse process to confirm the needle's position. After the fascia is seen to be open, a local anesthetic volume of 0.5% bupivacaine (Buvasin, VEM Pharmaceuticals, Turkey) will be calculated as 2 ml per vertebral pressure, not exceeding a maximum dose of 2 mg/kg. This total volume will be diluted half and half with 0.9% NaCl solution to prepare a 0.25% bupivacaine concentration. The calculated local anesthetic solution will be administered to the erector spinae area for ESPB. The same procedures will be performed on the opposite side. No procedure will be performed on the control group. Both groups will receive 15 mg/kg Paracetamol (Parol®, ATABAY, Kurtköy, Pendik, İstanbul) intravenously 20 minutes before the end of surgery. After surgery, patients will be decurarized with 2 mg/kg IV sugammadex (Bridion, MerckSharpDohme, New Jersey, USA), extubated, and taken to the recovery unit. After being admitted to the recovery room, both groups will be assessed using the Wong-Baker FACES™ Pain Rating Scale for children under 5 years old and the FLACC: Pain Rating Scale for children 5 years and older, with pain scores at 0, 5, 10, 15, and 20 minutes. Patients with scores >5 will receive 0.5 mcg/kg fentanyl (TALİNAT®, VEM İlaç, Kapaklı/TEKİRDAG) for rescue analgesia. Paracetamol 15 mg/kg/6 hours will be administered intravenously for postoperative analgesia. A blinded investigator will assess patients' pain scores, analgesic requirements, names of analgesics administered, and nausea/vomiting at 30 minutes, 1, 2, 4, 6, 12, and 24 hours postoperatively. The time and dose of the first postoperative analgesic, and length of hospital stay will be recorded.

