
11. Research Budget

The cost of 34 block needles and 34 doses of the drug buvasin containing the active ingredient bupivacaine for one patient has been submitted with a propharmaceutical invoice. The expenses will be covered by the researchers.

12. Ethics Committee Approval

An application has been submitted for ethics committee approval.

13. Statistics

Statistical analyses of the obtained data will be performed using the IBM SPSS Statistics 21.0 software package. Descriptive statistics of the data will include mean, standard deviation, frequency, and percentage values. Chi-square and FischerExact tests will be used for the analysis of categorical variables. The normality assumption of continuous numerical variables will be checked separately in groups using the Shapiro-Wilk test. Analysis of variance (ANOVA) will be used for independent group

comparisons of numerical variables showing normal distribution. Kruskal-Wallis (KW) test will be used for variables that do not show normal distribution. For comparisons of consecutive measurements, the Wilcoxon Signed Ranks test will be used for pairs of measurements, the Friedman test for more than two measurements, and the Pearson correlation test will be used as a correlation test. The significance level will be set at $p<0.05$ in all analyses. The required sample size for the study was calculated as 68 (34+34) patients in total, including the group that underwent ESPB and the group that did not undergo ESPB, with an effect size of 0.70, 80% test power, and 95% confidence level. The relevant calculations were made in the G-Power 3.1.9.2 software package.

14. References

1. Gado, A. A., Alsadek, W. M., Ali, H., & Ismail, A. A. (2022). Erector spinae plane block for children undergoing cardiac surgeries via sternotomy: a randomized controlled trial Anesth Pain Med. 2022;12(2):e123723. doi: 10.5812/aampm-123723. PMID: 35991776
2. Aksu, C., & Gürkan, Y. (2018). Ultrasound guided erector spinae block for postoperative analgesia in pediatric nephrectomy surgeries. J Clin Anesth. 2018 Mar;45:35-36 doi: 10.1016/j.jclinane.2017.12.021. Epub 2017 Dec 20. PMID: 29274546

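### The only method named for repeated measurements is within-patient; how the two arms are compared on repeated pain scores is left unspecified, with no primary time and no multiplicity rule

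*Combined protocol and SAP*

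**What the plan says.** Section 13 (Statistics) has two sets of tests for numerical data. Independent groups are compared by ANOVA, or by Kruskal-Wallis if the data are not normal. Repeated data, which the plan calls consecutive measurements, have their own sentence: "the Wilcoxon Signed Ranks test will be used for pairs of measurements, the Friedman test for more than two measurements". On error control it says only "The significance level will be set at $p<0.05$ in all analyses". On size it says "The required sample size for the study was calculated as 68 (34+34) patients in total", "with an effect size of 0.70, 80% test power, and 95% confidence level"; the 0.70 is tied to no outcome or time.

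Section 10 (Material – Method) sets the schedule. Pain is scored five times in the recovery room (0, 5, 10, 15 and 20 minutes) and then by a blinded investigator "at 30 minutes, 1, 2, 4, 6, 12, and 24 hours postoperatively", which makes 12 times. Heart rate, pressures, SpO₂, ETCO₂ and BIS are recorded before surgery, at the "peroperative 5th, 10th, 15th, 30th, 60th, 90th, 120th, 180th minute" and after extubation, which makes ten times.

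The plan does not say which variables count as consecutive measurements, whether Friedman is run by arm or on all children together, or whether the independent-group tests are repeated at each time. It names no model with an arm-by-time term, no primary time, no multiplicity rule and no rule for missing values.

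**The concern.** Section 2 (Objective) includes less pain with ESPB over the first 24 hours. That is a difference between arms across a series of scores. The sentence written for series of scores names only tests that ask whether a child's values change over time. A significant Friedman result would say that pain rose or fell after surgery, which is expected with or without a block.

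The between-arm comparison is therefore left to the independent-group tests, whose use on 12 scores per child is not described. The analyst could test every time, pick one time, or average, and could decide after seeing the data. A claim about 24-hour pain could then rest on whichever time happened to fall below 0.05.

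**Working it through.** **1. The plan's own figure.** Inputs from Section 13: effect size 0.70, 80% power, 95% confidence, 34 per arm. Assumed, because not stated: 0.70 is a standardised mean difference d, and the test is a two-sided two-sample t test. Noncentrality is d × √(n/2) = 0.70 × √17 = 2.89 on 66 degrees of freedom, which gives power 81.2%. With 33 per arm power is 79.97%, so 34 is the smallest number that reaches 80%. The 68 is reproduced, and it is the size for one between-arm comparison of one value per child.

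**2. What Friedman responds to.** Simulation with 34 per arm, 12 times, 1,000 runs and an assumed within-child correlation of 0.5:

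| Scenario | All children | ESPB arm | Control arm |
|---|---|---|---|
| Real 0.70 SD ESPB shift at every time, no time trend | 5.5% | 3.9% | 5.3% |
| No ESPB effect, common decline over time | 100% | 100% | 100% |

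The entries are rejection rates at 0.05. With a real treatment effect the test rejects at about its nominal level; with no treatment effect but a time trend it always rejects.

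**3. Between-arm tests at every pain time.** With k = 12 tests at 0.05 and no true difference:

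- Independent times: 1 − 0.95^12 = 0.460, or 46%.
- Equal correlation ρ between times, normal approximation: 1 − E[{Φ((1.96 − √ρ·Z)/√(1−ρ)) − Φ((−1.96 − √ρ·Z)/√(1−ρ))}^12], with Z standard normal. At ρ = 0.5 this is 32%; simulations at 34 per arm fall between 32% and 37%. At ρ = 0.7 and 0.9 the formula gives 23% and 13%.
- Bonferroni over 12 times (0.05/12 = 0.0042) lowers power at one time for d = 0.70 to 51% by the normal approximation (47% by the noncentral t).

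**4. One contrast over 30 minutes to 24 hours.** Take the mean of the seven scores, with a shift of 0.70 SD at each time (assumed) and equal correlation ρ (assumed). The variance of the mean, relative to one score, is (1 + 6ρ)/7. The effective d is 0.70/√[(1 + 6ρ)/7]. Power is for a two-sided t test at 0.05 with 34 per arm.

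| ρ | Relative variance | Effective d | Power |
|---|---|---|---|
| 0.3 | 0.400 | 1.11 | 99% |
| 0.5 | 0.571 | 0.93 | 96% |
| 0.7 | 0.743 | 0.81 | 91% |
| 0.9 | 0.914 | 0.73 | 84% |
| one time only | 1 | 0.70 | 81% |

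**5. Vital signs only.** Friedman needs a value at every time. A child whose operation ends before 180 minutes has no 180-minute intraoperative value and drops out of that series. The documents give no operation duration, so the loss cannot be computed. If 10%, 30% or 50% of operations ended earlier (assumed), 34 × 0.9, 34 × 0.7 or 34 × 0.5 leaves about 31, 24 or 17 children per arm, selected by length of operation.

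**The case against.** The strongest objection is that the plan does contain between-arm tests. A pain score at a given time is a numerical variable, so ANOVA or Kruskal-Wallis can compare the arms there. Kruskal-Wallis has about 79–81% power for a 0.70 SD shift at one time. The sentence on consecutive measurements can be read as answering a separate, within-patient question, and nothing in it says that Friedman is meant to show a treatment effect. This stands. A reader might infer that the plan cannot detect an effect of ESPB on pain at all; Section 13 does not support that.

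Two other stronger readings also fail. A reader might expect Friedman to be run by arm and a result significant in one arm only to be read as a treatment effect. That would be a misuse, but the plan does not state it, and the documents give no basis for putting a probability on it. A reader might also link the 180-minute value to the pain result. Pain is scored after surgery at times that do not depend on the length of the operation, so that loss concerns the vital-sign series alone.

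It is also fair that pain level is one objective among several. Section 3 (Hypothesis) names intraoperative drug consumption and need for analgesia, which the planned tests can handle as totals or proportions. That pain scores and vital signs are the consecutive measurements is an inference, though no other outcomes in Section 10 fit as well.

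What the objection does not remove is that the use of the independent-group tests on 12 scores per child is unstated.

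**Conclusion.** The point holds as a gap in specification. Section 13 does not say how repeated pain scores are compared between arms, and the only tests it names for repeated data cannot make that comparison. If the gap is filled by testing each of the 12 times at 0.05, the chance of at least one false positive is 46% under independence and about 32–37% at correlation 0.5, and lower if scores within a child are more strongly correlated. Correcting by Bonferroni would leave about 51% power at any one time.

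A single prespecified contrast avoids that trade-off, with 84–99% power under a constant 0.70 SD shift and correlations from 0.9 down to 0.3. These power figures are conditional: the plan does not attach 0.70 to pain, and an effect that fades within 24 hours would give a smaller average. They show that 68 children suffice for the contrast under those assumptions; they do not show an error in the stated sample size. The vital-sign loss is real in kind and unknown in size. The change is worth making because it is cheap and uses data already scheduled.

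**What to change.** In Section 13, for postoperative pain, name one between-arm contrast over 30 minutes to 24 hours. Either of these would do:

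- a mixed model with arm, time, arm-by-time, age band (because Section 10 assigns the pain scale by age) and a patient random effect, reporting the time-averaged arm difference with a 95% CI; or
- the planned Kruskal-Wallis test on each child's mean score over the seven times.

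State how the recovery-room scores (0–20 minutes) are handled, since the contrast leaves them out. Label Friedman, Wilcoxon and per-time arm comparisons as descriptive. For vital signs, use all available values or limit the series to times that all children reach. A model does not make a 180-minute value meaningful for an operation that has already ended.

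The cost is a few sentences and a standard SPSS procedure, with no added patients or assessments. The downside of the mixed model is that it treats ordinal scores as approximately continuous; the rank test on each child's mean can serve as the check.

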and impaired functional recovery. Despite good progress in pain management, ineffective postoperative pain management in children remains a global problem. Regional anesthesia is increasingly used in pediatric patients to provide postoperative analgesia and support intraoperative anesthesia. Ultrasound-guided erector spinae plane block (ESPB) is a new approach. First introduced in 2016 by Forero et al., ESPB is a novel regional anesthesia technique that blocks branches of spinal nerves by injecting a local anesthetic into the fascial plane between the erector spinae muscle and the transverse process. Although new, ESPB has become quite popular due to its ease of application and reliability as a relatively superficial block. Initially, ESPB was defined for chronic pain from the thoracic region. Later, its indications expanded and it is now used in both acute and chronic pain conditions. Applications have also been reported in the lumbar, cervical, and sacral regions, respectively. In recent years, an increasing number of randomized controlled trials (RCTs) have reported that it provides effective postoperative analgesia for thoracic surgeries, nephrectomy, inguinal hernia repair, and laparoscopic cholecystectomy operations in children. In our study, we planned to evaluate the effect of bilateral ESPB on intraoperative anesthetic drug consumption and postoperative pain score and analgesia requirement in pediatric patients operated on due to tethered cord syndrome.

2. Objective

In our study, we aimed to reduce intraoperative anesthetic drug consumption and the level of pain in the first 24 hours postoperatively, the need for analgesics, and unwanted side effects related to analgesics by applying bilateral ESPB in pediatric patients operated on due to tethered cord syndrome.

3. Hypothesis

Bilateral ESPB reduces intraoperative anesthetic drug consumption and the need for postoperative analgesia in pediatric patients operated on due to tethered cord syndrome.

4. Study Phase and Nature

Low-risk scientific study - Prospective randomized controlled single-blind clinical trial

5. Study Population

Pediatric patients undergoing surgery for elective tethered cord syndrome

6. Inclusion Criteria

- Patients whose parents consented to participate in the study
- Patients aged 18 and under
- ASA (American Society of Anesthesiologists) physical status I, II, and III
- Pediatric patients undergoing elective tethered cord syndrome surgery

7. Exclusion Criteria

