- Patients whose parents did not consent to participate in the study

- Patients with ASA physical status IV and V

- Use of anticoagulant medications

- Allergy to local anesthetic drugs

- Patients with a history of gastrointestinal bleeding

- Patients with infection in the area where the block is planned

8. Study Center

Health Sciences University Bursa High Specialization Training and Research Hospital Anesthesiology and Reanimation Clinic

9. Study Duration

1 year

10. Material – Method

Patients included in the study will be divided into 2 groups according to the randomized (closed envelope) sampling method; Erector Spina Plane Block (ESPB, n=34) group and Control group (CG, n=34). Patients who regularly take medication due to cardiovascular or other systemic diseases will continue their medication. Those whose coagulation parameters are checked before the operation and are normal will be included in the study.

The patients' age, height, weight, gender, additional diseases, ASA scores, operation and anesthesia duration, operation level, level of block performed in the group undergoing ESP block, and total anesthetic drug consumption will be recorded. Standard ECG, SpO₂, non-invasive blood pressure (invasive blood pressure monitoring in necessary cases), EtCO₂ and BIS monitoring will be applied in the operating room. After appropriate intravenous access is established in both groups of patients, anesthesia induction will be achieved with 2 mg/kg propofol (Propofol 2%®, FreseniusKabi, Melsungen, Germany), 1 µgr/kg fentanyl (Fentanyl Citrate®, Hospira, USA), and 0.6 mg/kg rocuronium (Esmeron®, Organon, Kloosterstraat, Netherlands). Following intubation, anesthesia maintenance will be administered with a 2 l/min flow rate of 50/50 O₂/air mixture. Inhalation anesthetics will not be used, and no additional doses of muscle relaxants will be given. Neuromonitoring will be performed on all patients by the neurosurgical team following intubation. Patients will be turned to the prone position once they are stable. For total intravenous anesthesia in patients undergoing neuromonitoring-based anesthesia maintenance, propofol will be infused at an initial target plasma concentration of 2.5-4 µg.ml⁻¹ (Medcaptain Shenzhen, Guangdong, CHINA, Elevated model FK/FD). Remifentanil (ULTIVA®, GlaxoSmithKline Parma, Italy) will be infused at a rate of 0.5-1 µg/kg/min. Infusions will be maintained to maintain a BIS of 40-60. Preoperative,

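### No primary endpoint is named and the 0.70 effect size belongs to no outcome, so the 80% power attaches to no identified endpoint and the between-arm pain comparison is left open

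*Combined protocol and SAP*

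**What the plan says.** No outcome is called primary or main anywhere in the document.

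- **Title:** it points to postoperative pain.
- **Section 3 (Hypothesis):** "Bilateral ESPB reduces intraoperative anesthetic drug consumption and the need for postoperative analgesia in pediatric patients". These are two parts, and pain scores are not among them.
- **Section 2 (Objective):** "we aimed to reduce intraoperative anesthetic drug consumption and the level of pain in the first 24 hours postoperatively", followed by analgesic need and analgesic side effects. That makes four targets, unranked.
- **Section 10 (Material – Method), drug use:** "total anesthetic drug consumption will be recorded". Propofol and remifentanil are both infused; no unit or normalisation is given.
- **Section 10, analgesic need:** the blinded investigator records requirement and drug names, and in addition "The time and dose of the first postoperative analgesic, and length of hospital stay will be recorded".
- **Section 10, pain:** recovery-room assessment "with pain scores at 0, 5, 10, 15, and 20 minutes", then pain, analgesic requirement and "nausea/vomiting at 30 minutes, 1, 2, 4, 6, 12, and 24 hours postoperatively". The instrument depends on age: the Wong-Baker FACES "Pain Rating Scale for children under 5 years old and the FLACC: Pain Rating Scale for children 5 years and older".
- **Section 13 (Statistics):** "The significance level will be set at $p<0.05$ in all analyses". ANOVA or Kruskal-Wallis is named for numerical variables between groups, and chi-square and Fisher's exact test for categorical ones. Wilcoxon signed-rank and Friedman are named for consecutive measurements. The sample size of 68 (34+34) rests on an effect size of 0.70, 80% power and 95% confidence. No outcome, time point, expected means, SD, source, test family or sidedness is given.

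**The concern.** A power statement means something only for a defined variable and a defined test. Here neither part of the hypothesis is a single variable. Drug consumption covers at least two infused drugs. Analgesic need could be a yes/no requirement, a time to first analgesic, or a dose. If the investigators settle on a yes/no version, an effect size in SD units does not apply at all.

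The plan also does not say what counts as success. Whether one or both hypothesis parts must be significant decides whether the problem is excess false-positive error or a shortfall in power.

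For pain, the tests named for repeated measurements compare times within patients, not one arm with the other. ANOVA and Kruskal-Wallis are valid for two arms, but nothing says which of the 12 times, or what summary of them, they are applied to. The deciding comparison could therefore be picked once the results are known.

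**Working it through.** **1. Reproduce N=68.** Inputs from section 13: effect size 0.70, power 0.80, alpha 0.05, equal arms. Reading 0.70 as Cohen's d in a two-sided two-sample t-test is my assumption.

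- Noncentrality = d × √(n/2) = 0.70 × √17 = 2.886; df = 66; critical t = 1.997.
- Power: 33 per arm 79.97%, 34 per arm 81.2%. The solution is n = 33.02, rounded up to 34, giving 68. This matches.
- Other readings do not match: one-sided t-test 52 in total; ANOVA with f=0.70 about 18 in total. ANOVA with f=0.35 is the same as d=0.70 and also gives 34 per arm.
- Kruskal-Wallis on normal data at d=0.70 and 34 per arm: 79% (simulation).

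**2. Two hypothesis parts, each tested at 0.05, 34 per arm.** The documents give no correlation between the parts, so I take 0 to 0.8. Values at non-zero correlation come from simulation.

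| Success rule | Quantity | Correlation 0 | Correlation 0.8 |
|---|---|---|---|
| Either part suffices | False-positive rate | 1 − 0.95² = 9.75% | about 7.8% |
| Either part suffices | Power, d=0.70 on both | 96% | 88% |
| Both required | Power, d=0.70 on both | 0.8116² = 66% | 74% |
| Both required | Power, d=0.70 and 0.50 | 0.8116 × 0.5285 = 43% | 52% |
| Both required | Power, d=0.70 and 1.0 | 80% | 81% |
| Both required | Power, d=0.80 on both | 81% | 86% |

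When both are required, the error is at or below 5%. The shortfall in joint power disappears at about d=0.79 on both parts (uncorrelated).

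**3. Pain.** Section 10 gives 5 recovery-room times (0, 5, 10, 15, 20 min) and 7 later ones (30 min; 1, 2, 4, 6, 12, 24 h), 12 in all. As an illustration only, suppose the arms were compared at every time at 0.05. The chance of at least one false positive is about 40%, 32% or 24% at an assumed equal correlation of 0.3, 0.5 or 0.7.

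**4. Yes/no endpoint.** The control rates are assumed, and the block is assumed to halve them. Exact binomial power at 34 per arm:

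| Control vs block | Fisher | Uncorrected chi-square |
|---|---|---|
| 50% vs 25% | 49% | 59% |
| 60% vs 30% | 62% | 70% |
| 70% vs 35% | 76% | 83% |

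**5. What 80% power would need in other cases.**

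- Yes/no endpoint, Fisher: about 64 per arm (50% vs 25%) or 48 per arm (60% vs 30%).
- Both numerical parts required, uncorrelated: 44 per arm at d=0.70 on both (43 gives 79.9%, 44 gives 81.2%), and about 67 per arm at d=0.70 and 0.50.

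**The case against.** The strongest reply is that the plan is less loose than it looks. N=68 follows from its inputs. The 5% level has a clear referent, namely each analysis. The hypothesis joins its parts with an *and*; read plainly, both must succeed, and then the error does not exceed 5%. The title shows that pain is the main interest.

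Much of this stands, and it rules out some stronger readings.

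- A reader might infer that N=68 is miscalculated. It is not.
- A reader might infer that the 5% level is undefined. It applies per analysis; only a familywise rule is missing.
- A reader might infer that the trial runs at nearly 10% error. That needs an either-part success rule, which the text does not state.
- A reader might infer that 12 separate pain tests are planned. The plan does not say so, and the 24% to 40% range rests on assumed correlations.

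The rest does not rescue the plan. If both parts are required, the 80% figure is not the power of the claim being made unless the effects exceed 0.70. The title fixes no time point, scale or summary, and the hypothesis does not mention pain scores.

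**Conclusion.** The concern holds and should be resolved before outcome data are seen by group. No endpoint is primary, 0.70 is tied to none, and the between-arm pain comparison is unspecified. The stated 80% power (81% on recalculation) is right for one numerical outcome with d=0.70, but that outcome is not identified.

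The size depends on a choice the plan has not made. Under an either-part rule, the cost is up to 4.75 percentage points of extra false-positive error. Under a both-parts rule at d=0.70, joint power falls 6 to 14 points short of 80%. For a yes/no endpoint, power at 34 per arm ranges from 49% to 83% over the rates and tests considered. These figures rest on reading 0.70 as Cohen's d, on two-sided testing, and on correlations and control rates that the documents do not supply. The core gap depends on none of them.

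**What to change.** Before any outcome data are seen by group:

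1. **Primary endpoint.** In sections 3, 10 and 13, name one endpoint as one defined variable with its unit, time window and one between-arm test at two-sided 0.05. The investigators choose it; pain, analgesic need and drug consumption are all options.
2. **Effect size.** State the metric, test and sidedness behind 0.70, tie it to that endpoint and justify it. If the endpoint is yes/no, name the test and restate the power from its own calculation.
3. **Multiplicity.** Test any other outcome for which a confirmatory claim is wanted in a fixed sequence or by Holm, and label the rest secondary or exploratory. With two endpoints at d=0.70 each, a fixed sequence gives 81% for the first and 66% to 74% for the second; Holm gives 77% to 79% for each. If both hypothesis parts must succeed, state the joint power and its assumptions in place of 80%.
4. **Pain.** Pre-state one between-arm summary or model, for example a time-weighted AUC, or arm, time and arm-by-time, that accounts for the age-dependent scale.

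**Cost.** The change is wording in three sections. Section 12 says the ethics application is already submitted, so the committee may need to be notified. Fewer outcomes can be called significant. Randomisation is not stratified by age, so the age strata may be small.

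N can stay at 68 with the power restated, but that power may be well below 80% for a yes/no endpoint or a smaller effect. If 80% is wanted there, N rises. A limit of 44 per arm for 80% joint power holds only for two numerical endpoints, each with d of at least 0.70.
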